## 5.0 Risk management

All clinical testing (physical, serological and radiological) performed within this study is within the remit of standard clinical care and therefore the study itself will not put the participant at additional risk of medical complications or side-effects.

For qualitative data collection, validated scoring tools will be used wherever possible.

Both treatment pathways (A & B) observed in this study constitute routine surgical practice, with both techniques routinely used at ABMUHB. Both are gold-standard treatment with subtle differences in technique; neither is experimental in any way. Consequently any clinical complications can be dealt with in the normal clinical manner, regardless of the study.

It will be made clear to participants from the start of their involvement that they are free to withdraw from the study at any time, without any reason and without any impact upon their standard of care. Participants will be given the contact details for the study team, with their primary link being their centre’s PI who will supervise both their clinical care and data collection throughout the study period.

Should clinical need require deviation from the study protocol and subsequent exclusion as to avoid confounding effects on study results, this will be disclosed and reported in the results. Where it is felt that any data collected was unaffected by this process, it will be used wherever feasible.

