# 3.0 Study aims and objectives

## 3.1 Primary outcome

Primarily, the study aims to evaluate:

1. Predictability and resultant dimensional accuracy of mandibular reconstructions performed using:
  - Fibular free-flap reconstruction of the mandible with a customized pre-flexed mandibular reconstruction plate and cutting guides (Treatment pathway A)

OR

1. Fibular free-flap reconstruction of the mandible with a customized SLM mandibular reconstruction plate and cutting guides (Treatment pathway B)

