## 3.2 Secondary outcomes

Secondarily, the study aims to compare treatment pathways A and B for:

2. The duration of surgery (in particular individual components of the surgery such as flap warm ischaemia time, duration of osteotomies and plate fixation procedures.

3. The operators' perceptions of the overall intraoperative usability, confidence with the technique and immediate satisfaction of the surgical result.
4. The need to make minor adjustments to either the plate, osteotomy or screw holes in order to fit the plate during surgery.
5. Incidence of postoperative complications (as recorded during inpatient stay as well as at 6 weeks, 6 months and 1 year outpatient follow up visits), for example:
  - a. Localised infection
  - b. Plate extrusion/exposure
  - c. Length of hospital stay (including duration of intensive care / high-dependency / ward requirements)
  - d. Mal / non / delayed-union of the bony components of the mandibular reconstruction (from objective analysis of clinically routine postoperative CT scan imaging)
  - e. Plate fractures/failures
6. Medium-term (up to 1 year) functional outcomes, for example:
  - a. Feasibility of dental implant rehabilitation (specifically in the technical context of clinical and/or radiological perspective of bone quality and anatomy as well as in the holistic context of the patient's suitability overall, in order to determine the importance of reconstructed bony anatomy in the decision processes and planning of dental rehabilitation)
  - b. Objective evaluation of changes in dental occlusion (with the aid of dental model analysis).
  - c. Objective assessment of changes in facial aesthetics (facial symmetry based upon baseline and postoperative 3D photography (stereophotogrammetry).
7. Patient-perceived quality of life:
  - a. using a validated quality of life assessment tools:
    - i. University of Washington Quality of Life Questionnaire v4
    - ii. Short-form Derriford appearance scale (DAS24)
    - iii. Liverpool oral rehabilitation questionnaire
  - b. by time to return to work / social status at 1 year (where applicable)
8. Economic implications (with economic analysis taking the above clinical and social outcomes into account).

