**Perioperative / inpatient data collection (CRF02 form).**

- Prior to commencing surgery, bite registration to be obtained (using viscoelastic silicone impression putty)
- At surgery, record of:
  - Times at which mandibular osteotomies are first started (cutting guides first placed onto mandible) and completed
  - Time of knife-to-skin for flap harvest
  - Time of flap detachment
  - Time of completing fixation of the plate (with flap) in its final resting position (i.e. when completion of fixation to the residual mandible)
  - Time of completing arterial anastomosis
- Record of need for any intraoperative adjustment to the plate, osteotomies and/or planned drill hole positions.
- Surgeon rating of usability, confidence of use, satisfaction with reconstructive procedure.
- Scrub nurse rating of usability, confidence of use, satisfaction with reconstructive procedure.
- Record of days-stayed on ITU / HDU and/or Ward, date of discharge.
- Record of all complications as inpatient (peri & post operative).

**6 weeks follow up** (CRF03 form).

- Physical assessment (BMI, oral hygiene status).
- University of Washington QoL questionnaire.
- Short-form Derriford appearance scale (DAS24).
- Liverpool oral rehabilitation questionnaire.
- Report on complications.
- 3D Photograph (Stereophotogrammetry) of the head and neck.
- Detailed social history (e.g. current occupation / employment)

**6 months follow up** (CRF04 form).

- Data recorded as per CRF03 form.
- Postoperative CT mandible scan (evaluation of actual vs. planned dimensions, quantitative evaluation of bony cortical union at osteotomy sites)

**1 year follow up** (CRF05 form).

- Data recorded as per CRF03 form.
- Dental assessment (including routine cone beam CT scan) and restorative dentist rating of technical and practical feasibility of prosthetic rehabilitation options

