#### 4.5.3 6 months follow up

The "6 months case report form" (CRF04) will be used to collect identical data to that collected at 6 weeks follow-up. This follow up point is selected as in the case of cancer surgery, it is a standard follow-up point for assessment of signs of early disease recurrence. For this reason, routine medical CT scanning to evaluate for disease recurrence is performed. A 3D render of DICOM data from this clinical scan can be used to dimensionally and volumetrically compare the actual bony reconstruction with the preoperative plan, evaluating overall accuracy and precision of the reconstructive technique used. Furthermore, CT assessment of bony union will be performed using a quantitative numerical rating score, adapted from Akashi et al.(Akashi et al., 2015)

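### The undefined exclusion rule in section 5.0 could take cases out of the primary CT accuracy comparison because of an event that follows the choice of pathway and is related to the outcome

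*Protocol*

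**What the plan says.** The protocol's Risk management section (5.0) contains this conditional rule: "Should clinical need require deviation from the study protocol and subsequent exclusion as to avoid confounding effects on study results", followed by the undertaking that "this will be disclosed and reported in the results". The next sentence deals with what is kept: "Where it is felt that any data collected was unaffected by this process, it will be used wherever feasible". The section does not list the deviations covered. It does not say who decides, when, or with what knowledge of pathway and result.

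The primary outcome (section 3.1) is "Predictability and resultant dimensional accuracy of mandibular reconstructions performed using" one or the other type of customised plate with its cutting guides. Predictability is not defined separately. The measurement is described under the 6-month follow-up in section 4.5.3, where the routine CT is used to "dimensionally and volumetrically compare the actual bony reconstruction with the preoperative plan".

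Under section 4.4 the surgeon chooses the pathway before the operation, once the virtual plan exists.

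Related events are collected elsewhere. Section 3.2 lists "The need to make minor adjustments to either the plate, osteotomy or screw holes in order to fit the plate during surgery" (item 4) and "Plate fractures/failures" (item 5e), with plate extrusion or exposure as item 5b. In Figure 1, the CRF02 box includes "Record of need for any intraoperative adjustment to the plate, osteotomies and/or planned drill hole positions".

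**The concern.** The rule's stated purpose is to prevent confounding. Confounding arises from differences between patients that precede the choice of pathway and influence both that choice and the result. A deviation forced by clinical need during or after surgery comes later than the choice and may be a consequence of it. Removing a participant for such an event does nothing about confounding and can introduce selection bias.

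The bias matters most for the primary measure. If a customised plate or its guides had to be given up, the final reconstruction may well lie further from the preoperative plan than in a case that went smoothly. The CT deviation is also the measurement most likely to be judged affected, so it is the one most likely to be dropped. The remaining cases would then show the accuracy of operations that went to plan, not the accuracy obtained once a pathway had been chosen. If such departures are more frequent in one pathway, the comparison itself shifts.

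**Working it through.** The protocol gives no conversion rate, expected deviation, standard deviation or power figure, so there is nothing of its own to reproduce. The check is first a reading of the text and then an illustration on assumed inputs.

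**Order of events.** Choice of pathway (4.4), then operation and recovery, then CT at 6 months (4.5.3). A clinically required deviation during or after surgery falls between the choice and the outcome.

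**What could count as a deviation.** The study is observational and prescribes little beyond data collection. A missed visit or questionnaire is missing data and would not normally be described as confounding. A changed plate or abandoned guides might be. The text names neither, so the rule permits such an exclusion without requiring it.

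**What is recorded anyway.** Adjustments to plate, osteotomies and drill holes, plate fractures or failures, and extrusion are all collected. Complete abandonment of the plate or guides has no explicit field. Recording also does not guarantee inclusion: section 4.2 reports flap failures and still excludes those participants.

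**Weight of one exclusion.** The stated minimum is 10 per pathway (section 4.0), so one exclusion removes 1/10 = 10% of a pathway.

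**Chance that the rule comes into play.** With an assumed departure rate p, the chance of at least one affected case among 10 is 1 − (1 − p)^10.

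| Assumed p | Chance of at least one in 10 |
|---|---|
| 5% | 40% |
| 10% | 65% |
| 20% | 89% |
| 30% | 97% |

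**Effect on one pathway's mean.** Assume a mean deviation of 2 mm in unaffected cases and 5 mm in affected ones.
- Two affected of 10: (8 × 2 + 2 × 5)/10 = 2.6 mm with everyone kept, 2.0 mm after exclusion. The reported mean is too small by 0.6/2.6 = 23%.
- One affected of 10: (9 × 2 + 1 × 5)/10 = 2.3 mm against 2.0 mm.

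**Effect on the difference between pathways.** If affected cases deviate by an extra g mm, exclusion removes (pA − pB) × g from the difference in means, where pA and pB are the departure rates in pathways A and B.
- 20% v 5%: 0.15 × 1 = 0.15 mm at g = 1, and 0.15 × 5 = 0.75 mm at g = 5.
- 10% v 10%: 0 mm at any g. The difference is unchanged, although each pathway's own mean still looks better than it was.
- 10% v 20%: −0.10 × 5 = −0.5 mm at g = 5. The sign reverses.

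All rates and millimetre values here are assumptions. They show that a handful of exclusions can matter at this sample size, not that they will.

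**The case against.** A reader might infer that section 5.0 removes plate failures and conversions from the study. The documents do not support that, for four reasons.

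- The wording concerns departure from the study protocol, not from the surgical plan. In an observational study that leaves treatment to the surgeon, an intraoperative change is not plainly a protocol deviation.
- The sentence is conditional. It does not say that every deviation leads to exclusion.
- Plate failures and extrusion are named secondary outcomes, and CRF02 asks for any intraoperative adjustment, not only minor ones.
- Predictability is undefined, so it is an inference that it was meant to capture conversions.

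The rule also carries two safeguards: exclusions will be disclosed, and data thought to be unaffected will be used. That the decision would be made with knowledge of the pathway is likewise an inference. The protocol describes blinding only for participants and is silent on who decides.

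Two further arguments concern the remedy. A wider resection may be driven by disease, and scoring it against the original plan would blame the technique for something it did not cause. Analysis populations are also commonly settled in a statistical analysis plan, which is not at hand here.

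Most of this stands, and it confines the point to possible exclusion from the CT comparison. It does not dispose of it. The exclusion rule and its rationale are stated in the protocol itself, so this is not merely a detail left for later. Disclosure tells the reader that cases are missing but does not return them to the comparison. Retention by what is felt to be unaffected gives least protection to the CT deviation. The argument about disease-driven changes is a reason to record why the plan changed and to examine those cases separately, not to leave exclusion open.

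**Conclusion.** The point holds in a limited form. Section 5.0 states an open-ended exclusion after treatment, justified as avoiding confounding, that could remove from the primary accuracy comparison cases in which the planned plate or guides were abandoned or exchanged. That would be selection on an event after the choice of pathway and related to the outcome.

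Neither size nor direction can be fixed from the documents. The 23% understatement and the range from −0.5 to 0.75 mm rest wholly on assumed rates and deviations. They also assume that affected cases lie further from plan than the others. With equal departure rates and equal excess deviation in the two pathways, the between-pathway difference would not move. With about 10 participants per pathway, however, one or two such decisions are enough to alter the result visibly. The rule should therefore be settled before any outcome is seen.

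**What to change.** Replace the exclusion rule in section 5.0 with a statement that every operated participant with a 6-month CT stays in the primary comparison under the pathway chosen at section 4.4. Flap failure is handled by a separate rule in section 4.2, which this point does not examine.

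Add one item to CRF02: whether the planned plate and the planned guides were used, modified or abandoned, and the reason, separating device or fit problems from a disease-driven change of resection. Report this by pathway. A disease-driven change need not be scored as a failure of predictability.

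Present the analysis limited to cases where the plan was followed, and the one without disease-driven resection changes, only as sensitivity analyses beside the main result.

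The cost is a change of protocol wording and one CRF item, with no effect on clinical care. The small downside is a wider spread in the accuracy results, because the less tidy cases stay in.

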## 6.0 Statistical analysis

Data will be collated and analyzed using a statistical software package. Descriptive statistics will be used for baseline measures, categorical statistics for questionnaire outcome data, and relationships will be evaluated using tests of correlation and comparison, along with regressional analysis.

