## 4.0 Study design

JaW PrinT is a 'real-world' prospective observational pilot study, evaluating the clinical effectiveness, usability and economics of two approaches to mandibular reconstruction surgery (figure 1). Patient participants will be recruited prospectively over a minimum period of 18 months (with observation of at least 10 participants in each treatment pathway). The figures are based upon the historical clinical practice of the research site, with both techniques in equal use;

choice depending on resources, surgical training requirements and surgeon's clinical preference.

As a purely observational study, treatment choice will be made in the normal clinical manner and will in no way be influenced by the study itself.

Participants will be followed up at their routine outpatient clinics (6 weeks, 6 months and 1 year postoperatively) with prospective outcomes data collection (figure 1).

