#### **4.4 Treatment pathway allocation**

Upon recruitment, provision of informed consent and collection of baseline data, as per standard clinical practice, the patient participant's CT scan data is used to produce a virtual surgical plan for the mandibular resection and fibular free-flap reconstruction. Once the clinically optimal reconstructive surgical plan is established by the surgeon and technician, the choice of surgical approach will be made in the routine clinical manner by the surgeon: Pathway A (pre-flexed customized mandibular reconstruction plate and cutting guides) or to pathway B (SLM customized mandibular reconstruction plate and cutting guides). Both

treatment pathways are already part of routine/standard clinical practice at ABMUHB.

The expected/planned patient numbers for this study are based upon the historical workload of the Oral and Maxillofacial Surgery department at Abertawe Bro Morgannwg University Health Board (ABMUHB) of 10-20 cases annually. A recruitment period of 18 months with follow-up for 1 year fits within the time constraints of the postgraduate student investigator's PhD timeline.

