## 4.5 Study procedures

### 4.5.1 Baseline Assessment

This will be performed using a "baseline case report form" (CRF01), which will include past medical history (with attention to any history of previous radiotherapy to the head and neck region); a 'systems review' to screen for undisclosed comorbidities as well as smoking and alcohol status. The patient participant's comorbidity and performance status scores will also be recorded. The qualitative/subjective assessment of oral hygiene status (good/fair/poor) by a consultant oral and maxillofacial surgeon will also be recorded. Collected from routine clinical preoperative tests, BMI and serum albumin concentration will be recorded as an indicator of nutritional status, along with a full blood count, urea and electrolytes and clotting screen. Baseline quality of life assessment will be performed using the University of Washington QoL Questionnaire v4 (Rogers et al., 2002)(Appendix A). A baseline assessment of the participant's perceived appearance and oral function will be evaluated using the short-form Derriford appearance scale (DAS24) (Carr et al., 2005) which is suited as a research of appearance in H&N cancers (Djan and Penington, 2013), and the Liverpool oral rehabilitation questionnaire(Pace-Balzan et al., 2006) (Appendix B) respectively. Presurgical facial aesthetics will also be evaluated by means of assessing facial symmetry with stereophotogrammetry (clinical 3D photography in the medical illustration department) of the head and neck region.

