### 4.5.2 Perioperative/inpatient data collection

During the inpatient phase of the participant's medical treatment, all data will be recorded on the "inpatient case report form" (CRF02).

To evaluate the presurgical dental occlusion (if occluding teeth present), a bite registration will be taken whilst the patient participant is anaesthetised. These will be obtained using a viscoelastic silicone impression material.

At surgery, overall time from knife to skin, to transferring the patient participant off the operating table will be recorded. Furthermore the timings of specific landmarks of reconstructive components of surgery will be recorded:

- Times at which mandibular osteotomies are first started (when mandibular cutting guides first touches mandible) and completed (when mandibular cutting guides removed)

- Time of knife-to-skin for flap harvest
- Time of flap detachment
- Time of completing fixation of the plate in its final resting position (i.e. when completion of fixation to the residual mandible)
- Time of completing arterial anastomosis

To evaluate the impact of cutting guides on the fit of the bony flap, the surgeon will be asked to record the number of subsequent adjustments needed to the mandibular/fibular osteotomies, drill holes and/or the plate itself.

To further evaluate the efficiency of either surgical technique (and any potential 'learning curve' effect), the surgeon and scrub nurse will be asked to provide a 5-point Likert scale rating for the following criteria at the end of the operation:

- Ease of use
- Confidence in performing the technique
- Immediate satisfaction with reconstructive component of surgery

In the immediate postoperative (inpatient) phase of recovery, dates of stay in the intensive care unit (ITU), high dependency unit (HDU) and/or the inpatient ward will be recorded, along with a final discharge date. During this period, any postoperative complications are to be recorded if/as they occur.

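### Section 6.0 assigns categorical statistics to ordered, repeated questionnaire scores and does not tie its regression to those outcomes or to their baseline values

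*Protocol*

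**What the plan says.** Section 6.0 is the whole of the protocol's statistical text. On this point it states "Descriptive statistics will be used for baseline measures, categorical statistics for questionnaire outcome data", and the sentence goes on: "relationships will be evaluated using tests of correlation and comparison, along with regressional analysis". No outcome or covariate is attached to the second part.

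The questionnaires are outcomes for a between-pathway comparison. Section 3.2 opens with "Secondarily, the study aims to compare treatment pathways A and B for" and lists three instruments under patient-perceived quality of life: UW-QOL v4, DAS24 and the Liverpool oral rehabilitation questionnaire.

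All three are taken before surgery. Section 4.5.1 says "Baseline quality of life assessment will be performed using the University of Washington QoL Questionnaire v4" and adds the other two. They are repeated at 6 weeks. At 6 months the case report form "will be used to collect identical data to that collected at 6 weeks follow-up", and Section 4.5.4 says the same for 1 year.

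The pathway is not randomised. Section 4.4 says that "the choice of surgical approach will be made in the routine clinical manner by the surgeon", and Section 4.0 describes that "choice depending on resources, surgical training requirements and surgeon's clinical preference". Figure 1 and Section 4.4 both place baseline collection before this choice.

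**The concern.** The protocol is not silent here. It puts a method label on the questionnaire outcomes, and the label suits the data poorly. Scores with an order and a pre-treatment value carry more information than a category table uses. The baseline score is measured before the pathway is chosen, so it is a legitimate covariate. Section 8.0 lists the quality-of-life questionnaires among the few items that go beyond routine care, so patients complete them for the research.

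Two things are at stake. The first is precision, in a study whose stated minimum is ten patients per pathway. The second is bias: nothing in the design balances baseline scores between pathways, so an unadjusted comparison carries any systematic difference into the result. Both concern one secondary aim among several in an observational pilot. The primary outcome, dimensional accuracy, is not touched.

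**Working it through.** **No stated figure to reproduce.** The protocol gives no alpha, power, effect size, SD or correlation. The numbers rest on workload: 10 to 20 cases a year × 1.5 years = 15 to 30 in total, with at least 10 per pathway. I therefore looked at 10 per pathway, and at 15 (30 ÷ 2) as the upper end.

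**Form of the data (Appendices A and B).**

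- UW-QOL has 12 domain items and 3 general items, 15 in all. Six have five levels (pain, appearance, activity, recreation, mood, and the comparison with the month before cancer). Six have four (swallowing, speech, shoulder, taste, saliva, anxiety). One has three (chewing). Two have six (health-related and overall quality of life). 6 + 6 + 1 + 2 = 15.
- Liverpool has 33 items scored 1 to 4: items 1–17, 20–23, 26–31 and 34–39, so 17 + 4 + 6 + 6 = 33. Items 26–31 and 34–39 (12 of the 33) are answered only by patients with a denture or implant-retained teeth.
- Some questions are truly nominal: whether the patient has teeth, a denture or implants, and the choice of up to three most important issues.
- The DAS24 form is not printed, so its format cannot be checked.

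**Assumed inputs, not in the protocol.** Two-sided 5%; true difference d = 1 SD; baseline to follow-up correlation r = 0.3 to 0.7.

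**Formula check on a continuous score.** Adjustment multiplies the residual SD by √(1 − r²). Power ≈ Φ( d / (√(1 − r²) · √(2/n)) − 1.96 ). With n = 10, 1/√0.2 = 2.236.

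- Unadjusted: Φ(2.236 − 1.96) = Φ(0.276) = 61%.
- r = 0.3: Φ(2.236/0.954 − 1.96) = 65%.
- r = 0.5: Φ(2.236/0.866 − 1.96) = 73%.
- r = 0.7: Φ(2.236/0.714 − 1.96) = 88%.

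**Simulation on ordered levels.** A normal latent score is cut into four or five levels, with 10,000 data sets per setting. The unadjusted method is a rank test (Mann-Whitney), which already keeps the order. The adjusted method is a linear model with the baseline level as covariate. Clustered means that 60% of patients are at the top baseline level. The adjusted columns show power at each value of r.

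| Setting | Unadjusted | r = 0.3 | r = 0.5 | r = 0.6 | r = 0.7 |
|---|---|---|---|---|---|
| n = 10, four levels | 50–51% | 53% | 58% | 63% | 69% |
| n = 10, four levels, clustered | 50–51% | 52% | 56% | 58% | 64% |
| n = 10, five levels | 51–52% | 53% | 61% | 65% | 72% |
| n = 10, five levels, clustered | 51–52% | 53% | 58% | 61% | 66% |
| n = 15, five levels | about 70% | 73% | 79% | 83% | 89% |
| n = 15, five levels, clustered | 70–71% | 72% | 76% | 80% | 85% |

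With ten per pathway, the gain is about 1 to 2 points at r = 0.3 and about 5 to 20 points at r = 0.5 to 0.7. A rank-based adjusted analysis came within about 2 points of the linear model.

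**Bias.** Assume no true effect and a systematic baseline difference of 0.5 SD. On the latent scale the unadjusted false difference is r × 0.5, so 0.15, 0.25, 0.30 and 0.35 SD at r = 0.3, 0.5, 0.6 and 0.7. On a five-level score with n = 10 it was 0.14 to 0.33 SD unadjusted. After adjustment 0.01 to 0.03 SD remained, or 0.04 to 0.10 SD if clustered. The unadjusted false-positive rate rose from 6% at r = 0.3 to 11% at r = 0.7; adjusted (unclustered) it was 5% to 6%.

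**The case against.** The strongest reply is that the protocol nowhere says unadjusted. The same sentence of Section 6.0 provides for comparison tests and regression, and regression is the usual tool for baseline adjustment. Describing baseline measures is ordinary practice and does not stop anyone from using them as covariates. The label categorical statistics is undefined and may include ordinal methods, even ordinal regression with a covariate. Model details can properly sit in a statistical analysis plan that is not shown. All of this stands, and it makes the point conditional. What remains is that the one phrase that does name the questionnaires gives them a poorly fitting label, and the clause that could repair it is not connected to them.

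Three stronger readings are tempting, and the text supports none of them.

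- A reader might infer that nominal tests are planned. For a five-level item, d = 1 and ten per pathway, a nominal chi-square test had only about 22% power, against about 49% for a rank test. But the protocol does not define the label, so this larger loss cannot be charged to it.
- A reader might infer that baseline scores are to be described and nothing more. Section 6.0 contains no such restriction.
- A reader might infer that the pathways differ in baseline quality of life. The drivers of choice in Section 4.0 are resources, training needs and surgeon's preference, which do not include it. Whether scores differ is unknown.

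It is also fair to say that categorical methods suit some of the questionnaire content, and that a blanket baseline-adjusted rule would fail for patients who first receive a denture or implants after surgery and so have no baseline answer on 12 Liverpool items. The fix has to allow for both.

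**Conclusion.** The point holds as a minor one. Section 6.0 labels ordered questionnaire scores, measured four times, for categorical statistics and leaves the regression it mentions unconnected to them and to their baseline values. If the label is followed as an unadjusted comparison, the loss at ten per pathway is negligible at r = 0.3 and worthwhile at 0.5 to 0.7, and any systematic baseline difference passes into the result in proportion to r. These sizes depend on the assumed 1 SD effect, the assumed correlations, the assumed clustering at the top level and the assumed 0.5 SD imbalance. None of these comes from the protocol. No stated figure is wrong, and the result affected is exploratory.

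**What to change.** In Section 6.0, replace the phrase on questionnaire outcome data with wording such as:

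> Questionnaire scores with a baseline value are compared between pathways at each follow-up visit as ordinal or continuous scores, with the patient's baseline score as covariate. Adjusted differences with 95% confidence intervals are reported as exploratory, with a rank-based baseline-adjusted sensitivity analysis. Unadjusted ordinal methods are used where no baseline value exists (staff ratings, dental suitability rating, and Liverpool denture/implant items for patients without a baseline answer). Categorical methods are kept for nominal items (has-teeth/denture/implant questions, choice of most important issues).

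The staff ratings are those in Section 4.5.2, where "the surgeon and scrub nurse will be asked to provide a 5-point Likert scale rating"; the dental suitability rating is in Section 4.5.4.

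The cost is a few sentences, with no new data or visits. Scoring and model details for each instrument can stay in the statistical analysis plan. The downside is a model assumption in a small sample, largely covered by the rank-based analysis. If many patients score at the top at baseline, adjustment gains less and removes most but not all of the bias. In no case does adjusting for the baseline score remove other confounding by surgeon choice, and the report should say so.
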